### **Adverse Events of Special Interest**

For this study, AEs of special interest include any treatment-emergent neuropathy and suspected cases of PML (see Section [6.3.1.3](#) for reporting of AEs). These events will be followed until significant changes return to baseline, the event stabilizes or is no longer considered clinically significant by the Investigator, the subject dies or withdraws consent, or the study is closed.

Subjects who experience a Grade 2 neuropathy will have dosing withheld (see Section [5.1](#)); subjects with Grade 3 or higher neuropathy will be withdrawn from the study (see Section [4.4.4](#)).

See Section [6.3.3](#) for additional information on PML monitoring and Section [6.3.2](#) for management of infusion reactions.

### **Serious Adverse Event**

An AE should be classified as an SAE if it meets one of the following criteria:

- Fatal: The AE resulted in death.
- Life-threatening: The AEs placed the subject at immediate risk of death. This classification does not apply to an AE that hypothetically might cause death if it were more severe.
- Hospitalization: The AE required or prolonged an existing inpatient hospitalization. Hospitalizations for elective medical or surgical procedures or treatments planned before the signing of informed consent in the study or routine check-ups are not SAEs by this criterion. Admission to a palliative unit or hospice care facility is not considered to be a hospitalization. Hospitalizations or prolonged hospitalizations for scheduled therapy of the

underlying study target disease need not be captured as SAEs.

- **Disabling/ incapacitating:** The AE resulted in a persistent or significant incapacity or substantial disruption of the subject's ability to conduct normal life functions.
- **Congenital anomaly or birth defect:** The AE was an adverse outcome in a child or fetus of a subject exposed to the molecule or study treatment regimen before conception or during pregnancy.
- **Medically significant:** The AE did not meet any of the above criteria, but could have jeopardized the subject and might have required medical or surgical intervention to prevent one of the outcomes listed above or involves suspected transmission via a medicinal product of an infectious agent.

## **Adverse Event Severity**

Adverse event severity should be graded using the NCI-CTCAE, version 4.03. These criteria will be provided in the study manual.

The AE severity and seriousness are assessed independently. 'Severity' characterizes the intensity of an AE. 'Serious' is a regulatory definition and serves as a guide to the Sponsor for defining regulatory reporting obligations (see definition for Serious Adverse Event).

## **Relationship of the Adverse Event to Study Treatment**

The relationship of each AE to brentuximab vedotin should be evaluated by the Investigator using the following criteria:

- **Related:** There is evidence to suggest a causal relationship between the study drug and the AE, such as:
  - an event that is uncommon and known to be strongly associated with drug exposure (eg, angioedema, hepatic injury, or Stevens-Johnson syndrome); or
  - an event that is not commonly associated with study drug exposure, but is otherwise uncommon in the population exposed to the drug (eg, tendon rupture).
- **Unrelated:** Another cause of the AE is more plausible (eg, due to underlying disease

or occurs commonly in the study population), or a temporal sequence cannot be established with the onset of the AE and administration of the study drug, or a causal relationship is considered biologically implausible.

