population due to a reduced number of prior and/or ongoing myelosuppressive and/or neuropathic medications. Simulations based on a population pharmacokinetics (PK) model developed using data from oncology patients predict that the first proposed dose level of 0.3 mg/kg will achieve serum brentuximab vedotin ADC observed concentration at the end of the dosing interval ( $C_{trough}$ ) levels greater than the in vitro half-maximal inhibitory concentration ( $IC_{50}$ ) against Th1 cells with 94% probability, but is expected to achieve a  $C_{trough}$  greater than the in vitro  $IC_{50}$  against Th17 cells with only 11% probability, which may be insufficient to induce remission consistently in SLE. The fourth doses of 0.3, 0.6, 1.2, and 1.8 mg/kg given every 3 weeks are expected to achieve  $C_{trough}$  greater than the in vitro  $IC_{50}$  against Th17 cells with 22%, 48%, 72%, and 83% probability, respectively, the latter of which may be sufficient, in addition to Th1 inhibition, to translate into disease remission. Therefore, 4 doses of up to 1.8 mg/kg may be appropriate to achieve sufficient brentuximab vedotin exposures in patients with SLE. As such, this study will be the first to explore the effects and tolerability of escalating doses of brentuximab vedotin in SLE; it is anticipated that the results of this study will inform the design of a longer-term, efficacy-focused Phase 2 study, since SLE often requires chronic, maintenance therapy.

In oncology patients, the median time to onset of neuropathy with brentuximab vedotin was 12.4 (HL) to 15.0 (ALCL) weeks, and the majority of neutropenia (82%) occurred within the first 4 treatment cycles, during a 1.8 mg/kg every 3 weeks dosing regimen. Given this experience, the present study proposes to examine the tolerability of a 12-week course of brentuximab vedotin (4 doses when given every 3 weeks) in patients with SLE.

Since the efficacy and tolerability of brentuximab vedotin in SLE is unknown, and many of the AEs observed with brentuximab vedotin in the oncology population may coincide with disease manifestations of SLE (eg, neuropathy or leukopenia), this study will involve a placebo comparator in a randomized, double-blind fashion. The randomization scheme proposed is anticipated to produce a cohort of placebo-treated patients comparable in size with the brentuximab vedotin cohorts, analogous to previously executed studies in SLE.

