## 2.6 Risk Assessment

In 2011, brentuximab vedotin (ADCETRIS®) was approved for marketing in the US for the treatment of patients with HL and ALCL, and in 2012, the product label was revised to include a Boxed Warning for progressive multifocal leukoencephalopathy (PML) and a contraindication for concomitant use of brentuximab vedotin and bleomycin. The product label dated March 2016 may be found in [Appendix 4](#). Should the product label be updated during conduct of the current study, a revised version will be provided to the Investigators.

Primary safety concerns with brentuximab vedotin include peripheral neuropathy and neutropenia. In the pivotal trials in HL and ALCL, neutropenia of Grade 3 or higher developed after a median of 2 doses administered at 1.8 mg/kg every 3 weeks, while the median time to Grade 3 neuropathy was 36.1 to 38.0 weeks. Therefore, neutropenia appears to be a more sensitive measure of serious toxicity, and should be evident by 6 weeks in the majority of treated subjects.

A Safety Monitoring Committee (SMC) will review and evaluate unblinded interim safety data after the final subject of each cohort has been evaluated at the Day 43 (Week 6) visit. Initiation of enrollment at the next dose level will only commence after endorsement of the SMC. When available from each full cohort, the SMC will review all Day 85 safety data and may recommend that an already enrolled succeeding dose cohort be discontinued, or its treatment regimen truncated.

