#### **6.3.1.3 Reporting Periods for Adverse Events and Serious Adverse Events**

The safety reporting period for all AEs and SAEs is from date of consent through the follow-up visit. All SAEs that occur after the safety reporting period and are considered study treatment-related in the opinion of the Investigator should also be reported to the Sponsor. In addition, new-onset neuropathy, suspected PML, or other AEs/SAEs of interest will be reported until the end of the follow-up period.

Serious AEs will be followed until significant changes return to baseline, the event stabilizes (recovering/resolving) or is no longer considered clinically significant by the Investigator, or the subject dies or withdraws consent. All nonserious AEs will be followed through the safety reporting period. Certain nonserious AEs of special interest may be followed until resolution, return to baseline, the event stabilizes or is no longer considered clinically significant by the Investigator, the subject dies or withdraws consent, or study closure.

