19.1. ADVERSE EVENTS

An AE is any untoward medical occurrence in a patient or clinical investigational subject administered a medicinal product and which does not necessarily have a causal relationship with this treatment

Adverse Events (AEs) will be coded using MedDRA central coding dictionary, Version 18.0.

Treatment emergent adverse events (TEAEs) are defined as AEs that started or worsened in severity on or after the first dose of study medication.

Pretreatment AEs are defined as AEs occurring prior to dosing. These events will be presented in the listings only and are not included in the tabular summary of AEs.

See Appendix 2 for handling of partial dates for AEs. In the rare case where it is not possible to assess treatment emergence, the AE will be classified as treatment emergent (i.e. the worst case).

Severity

Adverse event severity will be graded using the NCI-CTCAE, version 4.03. TEAEs starting after the first dose of study medication with a missing severity will be classified as severe. If a subject reports a TEAE more than once within that SOC/ PT, the AE with the worst case severity grade will be used in the corresponding severity summaries.

Relationship to Study Medication

Relationship to study medication, as indicated by the Investigator, is classified as Related and Unrelated .A "related" TEAE is defined as a TEAE with a causal relationship between the study drug and the AE, such as:

- an event that is uncommon and known to be strongly associated with drug exposure (eg, angioedema, hepatic injury, or Stevens-Johnson syndrome); or
- an event that is not commonly associated with study drug exposure, but is otherwise uncommon in the population exposed to the drug (eg, tendon rupture).

An unrelated AE to study medication is defined as another cause of the AE is more plausible (eg, due to underlying disease or occurs commonly in the study population), or a temporal sequence cannot be established with the onset of the AE and administration of the study drug, or a causal relationship is considered biologically implausible.

TEAEs with a missing relationship to study medication will be regarded as "related" to study medication. If a subject reports the same AE more than once within a particular SOC/ PT, the AE with the highest level of relationship to study medication will be used in the corresponding relationship summaries.

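### The causality criteria offer no Related example for a common, known drug effect and cite commonness as a ground for Unrelated, so neuropathy and neutropenia risk under-attribution in the related-only outputs

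*Protocol*

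**What the plan says.** Protocol 6.3.1.1 (Relationship of the Adverse Event to Study Treatment) has two categories.

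- **Related** opens with a general test: "There is evidence to suggest a causal relationship between the study drug and the AE, such as". Two examples follow. The first is "an event that is uncommon and known to be strongly associated with drug exposure". The second is "an event that is not commonly associated with study drug exposure, but is otherwise uncommon in the population exposed to the drug".
- **Unrelated** applies when another cause is more plausible, when timing does not fit, or when causation is biologically implausible. The examples of a more plausible cause are underlying disease and commonness: "or occurs commonly in the study population), or a temporal sequence cannot be established".

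SAP 19.1 carries the same examples, including "another cause of the AE is more plausible (eg, due to underlying disease or occurs commonly in the study population". It takes relationship as the Investigator recorded it. SAP 19.1 and 19.1.2 then plan tables restricted to related TEAEs and related SAEs, and Protocol 8.6.1 also promises a summary of drug-related AEs.

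Protocol 2.6 states: "Primary safety concerns with brentuximab vedotin include peripheral neuropathy and neutropenia". Protocol 2.5 gives the overlap with lupus as part of the reason for a placebo arm: "many of the AEs observed with brentuximab vedotin in the oncology population may coincide with disease manifestations of SLE (eg, neuropathy or leukopenia".

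Protocol 6.3.1.3 sets the rule for later events: "All SAEs that occur after the safety reporting period and are considered study treatment-related in the opinion of the Investigator should also be reported".

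**The concern.** Commonness is not a cause. In a population whose disease can mimic the drug's toxicity, an Investigator who follows the examples literally has a written reason to call a neuropathy or a low white count unrelated, and no matching example for calling it related. The phrase about the study population is also ambiguous. It probably means lupus patients in general, but 32 of the 40 planned subjects receive active drug, so a toxicity made common by the drug could satisfy it.

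Safety and tolerability form the only primary objective, and the trial is meant to inform a larger study. If known drug effects are under-attributed, the related-only tables understate the toxicities of most interest. After the Day 127 follow-up visit, the relationship call also decides whether an SAE has to be reported.

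**Working it through.** The documents state no figure for this point, and the sample size rests on clinical judgment, so there is no planned calculation to reproduce. The check has three parts.

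**1. Do the examples cover a common, known drug effect?**

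- Related, example 1 requires an uncommon event, so an event the drug commonly causes does not plainly fit. The text does not say whether uncommon refers to background frequency or to frequency on drug.
- Related, example 2 requires an event not commonly associated with the drug. A known common effect fails this.
- The general test that introduces Related does cover such an event, but only through the Investigator's own judgement.
- Unrelated contains an example that a lupus-overlapping event can match.

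The SAP is tighter than the protocol. It drops the evidence test that opens Related and defines a related TEAE as one that has a causal relationship, followed by the same two examples.

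**2. Which outputs use the relationship call?**

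| Output | Depends on relationship? |
|---|---|
| Related TEAE tables (SAP 19.1) | Yes |
| Related SAE tables (SAP 19.1.2) | Yes |
| Reporting of SAEs after the follow-up visit (Protocol 6.3.1.3) | Yes |
| All TEAEs and SAEs by arm, including placebo (SAP 19.1, 19.1.2) | No |
| Neuropathy as an event of special interest (SAP 19.1.3) | No |
| Laboratory shifts by CTCAE grade (SAP 19.2) | No |
| SAE reporting within the reporting period (Protocol 6.3.1.4) | No |

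**3. How sensitive is a group of 8?**

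Inputs: 8 active subjects per dose (Protocol 5.3); peripheral sensory neuropathy 45% and neutropenia 21% (Protocol 2.3 and 2.5, oncology patients). Two assumptions are needed: that these rates apply here, and that a share m of drug-caused cases is labelled Unrelated. The documents give no value for m, so the whole range is shown.

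Expected related cases = 8 × p × (1 − m). Chance of at least one = 1 − [1 − p(1 − m)]^8.

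| m | Neuropathy (p = 0.45): expected | Chance of ≥1 | Neutropenia (p = 0.21): expected | Chance of ≥1 |
|---|---|---|---|---|
| 0% | 3.6 | 0.99 | 1.68 | 0.85 |
| 25% | 2.7 | 0.96 | 1.26 | 0.75 |
| 50% | 1.8 | 0.87 | 0.84 | 0.59 |
| 75% | 0.9 | 0.62 | 0.42 | 0.35 |
| 100% | 0 | 0 | 0 | 0 |

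For neutropenia at m = 50%: 8 × 0.21 × 0.5 = 0.84, and 1 − (1 − 0.105)^8 = 0.59, against 8 × 0.21 = 1.68 and 1 − 0.79^8 = 0.85 with no mislabelling. The outputs marked No in part 2 are the same for every m.

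**The case against.** The strongest reply is that the criteria permit Unrelated but do not force it. The Related examples are illustrative, and Unrelated on this limb needs another cause to be more plausible. Investigators also have written evidence pointing the other way. Protocol 2.6 describes neuropathy as an effect of cumulative exposure, the appended label says that the drug causes peripheral neuropathy, and Appendix 3 expects Investigators to know the Investigator's Brochure. This stands.

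A reader might infer that the related tables are biased toward zero, or that the related row could read 0 of 8. The documents do not support that. It would require every drug-caused case to be mislabelled, and nothing shows that any would be. Nor does a high oncology rate make an event common in lupus. The protocol gives no background rate, says only that events may coincide, and names leukopenia rather than neutropenia as the overlap. Entry criteria exclude known peripheral neuropathy and a neutrophil count below 1500/µL.

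The illustrative rates also have limits. They come from 1.8 mg/kg, which is one of four cohorts, and from longer courses than 4 doses. Protocol 2.5 reports no clinically significant neuropathy or neutropenia at 0.6 and 1.2 mg/kg. Protocol 6.3.1.1 generally keeps laboratory abnormalities without symptoms or intervention out of the AE record, so some neutropenia will never receive a relationship call.

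A reader might also infer that the main safety comparison is compromised. It is not: comparison by arm against placebo needs no attribution, and missing relationship is counted as related. The late-SAE gap is narrow. It concerns events starting after Day 127, which is 127 − 64 = 63 days, or nine weeks, after the last planned dose, and an event of special interest already present continues to be followed.

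What remains is the wording gap. These safeguards limit its effect but do not repair the related-only tables or the late reporting rule.

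**Conclusion.** The point holds as a risk of under-attribution. The criteria lack a Related example for a common, known effect of the drug and offer commonness as a ground for Unrelated, in a population where the protocol itself expects overlap. The direction, if any mislabelling follows, is toward fewer related events. The size is unknown.

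The illustrative fall for neutropenia, from 1.7 to 0.8 expected related cases of 8, rests on two assumptions that the documents do not establish: that the oncology rate carries over, and that half of drug-caused cases are called unrelated. It shows only that related-only counts in groups of 8 are sensitive to the wording. The consequence is confined to the drug-related TEAE and SAE tables and to SAEs starting after the follow-up visit. This is a cheap improvement and not a threat to the trial's main safety conclusions.

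**What to change.** Change Protocol 6.3.1.1, and put the same text in the CRF completion guide so that it reaches Investigators:

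1. Delete the example under Unrelated that treats commonness in the study population as another cause. Underlying disease can stay, since the governing test is that it must be more plausible.
2. Add a Related example: an event that the protocol identifies as a known effect of brentuximab vedotin (for instance peripheral neuropathy or neutropenia), whatever its frequency, with plausible timing and no more plausible specific alternative cause documented. Do not presume relatedness for every term in section 6 of the label. That list includes fatigue, rash, arthralgia and alopecia, and such a presumption would push the related tables toward the all-causality tables.
3. Align SAP 19.1 with this text and restore the protocol's opening test, "There is evidence to suggest a causal relationship between the study drug and the AE, such as". Changing the SAP alone would alter no data, because it uses the relationship as the Investigator recorded it.

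The cost is a few lines in the protocol, SAP and CRF guide, with no change to visits, samples or dosing. The downside is that somewhat more events, including some on placebo, will be called related. That can be read against the blinded placebo group.

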### **6.3.1.2 *Procedures for Eliciting and Recording Adverse Events***

Investigator and study personnel will report all AEs and SAEs whether elicited during subject questioning, discovered during physical examination, laboratory testing, and/or other means by recording them on the CRF and/or SAE Form, as appropriate.

#### **Eliciting Adverse Events**

An open-ended or nondirected method of questioning should be used at each study visit to elicit the reporting of AEs.

#### **Recording Adverse Events**

The following information should be recorded on the Adverse Events and Pre-existing Conditions CRF:

- description, including onset and resolution dates;
- whether it met serious criteria;
- severity;
- relationship to study treatment or other causality; and
- outcome.

#### **Diagnosis Versus Signs or Symptoms**

In general, the use of a unifying diagnosis is preferred to the listing out of individual symptoms. Grouping of symptoms into a diagnosis should only be done if each component sign and/or symptom is a medically confirmed component of a diagnosis as evidenced by standard medical textbooks. If any aspect of a sign or symptom does not fit into a classic pattern of the diagnosis, report the individual symptom as a separate AE.

Important exceptions for this study are adverse reactions associated with the infusion of study drug. For infusion-related reactions, do not use the NCI-CTCAE terms of 'cytokine release syndrome,' 'acute infusion reaction,' or 'allergic or hypersensitivity reaction.' Instead, record each sign or symptom as an individual AE. If multiple signs or symptoms

occur with a given infusion-related event, each sign or symptom should be recorded separately with its level of severity.

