### **6.3.2 Management of Infusion Reactions**

Infusion-related reactions may occur during the infusion of study treatment. The infusion should be administered at a site properly equipped and staffed to manage anaphylaxis should it occur. All supportive measures consistent with optimal subject care should be given throughout the study according to institutional standards. Supportive measures may include administering medications for infusion-related reactions.

Subjects who have experienced a Grade 1 or Grade 2 infusion-related reaction should be premedicated for subsequent infusions. Premedication may include acetaminophen and an antihistamine administered 30 to 60 minutes prior to each brentuximab vedotin infusion or according to institutional standards.

If anaphylaxis occurs, brentuximab vedotin administration should be immediately and permanently discontinued.

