## **6.4 Pharmacokinetic Measurements**

### **6.4.1 Plasma Concentrations**

Sensitive, qualified assays will be used to measure drug analytes, including brentuximab vedotin (ADC), total antibody (TAb), and MMAE concentrations in serum or plasma. These assays will include enzyme-linked immunosorbent assays and liquid chromatography/tandem mass spectrometry assays, as well as other assays if further characterization is required.

Samples for PK analysis will be collected within 30 minutes prior to study drug administration and at the end of infusion (within 5 minutes) on study drug administration days (Days 1, 22, 43, and 64). Samples will also be collected between the first and second doses on Days 2, 3, 8, and 15 at approximately the same time of day as the end-of-infusion sample on Day 1, if possible. Additional samples will be collected any time on the day of collection during the observation period (Days 85 and 106) and at the follow-up visit on Day 127.

Up to approximately 700 mL of whole blood will be obtained from each subject for PK, PD, and safety assessments during the study.

The following information will be captured for blood sample collection in each subject's CRF:

1. subject's number and initial;
2. time and date of dose administration; and
3. time and date of each blood sample collected for PK analysis.

Please refer to the Laboratory Manual for sample collection and storage procedures.

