#### *Infusion reactions*

Two cases of anaphylaxis were reported in the dose-finding trials. There were no Grade 3 or 4 infusion-related reactions reported in Studies 1 and 2; however, Grade 1 or 2 infusion-related reactions were reported for 19 patients (12%). In Studies 1 and 2, the most common adverse reactions ( $\geq 2\%$ ) associated with infusion-related reactions were chills (4%), nausea (3%), dyspnea (3%), pruritus (3%), pyrexia (2%), and cough (2%).

In Study 3, infusion-related reactions were reported in 25 patients (15%) in the ADCETRIS-treated arm and 3 patients (2%) in the placebo arm. Grade 3 events were reported in 3 of the 25 patients treated with ADCETRIS who experienced infusion-related reactions. No Grade 4 infusion-related reactions were reported. The most common adverse reactions ( $\geq 2\%$ ) associated with infusion-related reactions were nausea (4%), chills (4%), dyspnea (2%), headache (2%), pruritus (2%), rash (2%), back pain (2%), and vomiting (2%).

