All AE tabulations will be performed by treatment group and active-treated overall, and will include the number and percentage of subjects. All percentages will be based on the number of patients in the Safety Population. Incidence of TEAEs will be tabulated by the following:

- Across all System Organ Class (SOC) and Preferred Term (PT), By Severity Grade, by Relationship, by Leading to Discontinuation, and by Seriousness
- By System Organ Class (SOC) and Preferred Term (PT)
- By System Organ Class (SOC), Preferred Term (PT) and Severity Grade
- By System Organ Class (SOC), Preferred Term (PT) for AEs Related to study medication only

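### The plan specifies no flag, link or overall grade for infusion-related reactions, so their number and worst grade per dose cannot be derived reliably or by a pre-specified rule

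*Protocol*

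**What the plan says.** Protocol Section 6.3.1.2 (Diagnosis Versus Signs or Symptoms) generally prefers a unifying diagnosis but makes infusion reactions an explicit exception. Sites are told: "do not use the NCI-CTCAE terms of 'cytokine release syndrome,' 'acute infusion reaction,' or 'allergic or hypersensitivity reaction". In place of those terms the instruction is: "Instead, record each sign or symptom as an individual AE". When several signs occur with one infusion, "each sign or symptom should be recorded separately with its level of severity".

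The same section (Recording Adverse Events) lists what goes on the adverse event CRF page: "description, including onset and resolution dates", then whether the event was serious, its severity, its relationship to treatment and its outcome. Section 6.4.1 has the CRF capture "time and date of dose administration; and" the time and date of each PK sample.

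Section 6.3.2 speaks of reactions as graded wholes: "Subjects who have experienced a Grade 1 or Grade 2 infusion-related reaction should be premedicated for subsequent infusions". Section 5.7.2 makes such premedication optional where 6.3.2 recommends it. That is a separate point, and the two sections need to be reconciled.

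SAP Section 19.1 tabulates treatment-emergent events by system organ class, preferred term, severity, relationship, seriousness and discontinuation. Repeated events are reduced to the worst severity within the same class and term. SAP Section 19.1.3 adds a special-interest listing and summary, by class and term and overall. It covers neuropathy (including PML) and infusion site reactions, with local examples, found through a standardised MedDRA query.

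**The concern.** The primary objective is safety and tolerability (Section 3.1). Section 2.6 names infusion-related reactions, including anaphylaxis, among the warnings relevant to patients with SLE. The natural summary is how many subjects at each dose had a reaction and how bad the worst one was, set against placebo.

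The recording rule breaks each reaction into components, and neither document provides a way to put them back together. The signs then fall into preferred-term rows for common symptoms such as nausea, chills and dyspnea, which also occur for other reasons. The trial could finish without a pre-specified answer to a basic tolerability question.

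**Working it through.** **1. What the two documents supply for a reaction-level summary**

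| Needed | Supplied? |
|---|---|
| Mark that a sign belongs to a reaction | Not in the Section 6.3.1.2 item list |
| Link between signs of one reaction | Not listed |
| Onset time relative to the infusion | Event date only; infusion time is recorded (6.4.1) |
| Grade of the reaction as a whole | Not listed; each sign has its own grade |
| SAP rule that groups signs | None in 19.1; 19.1.3 covers infusion site reactions only |

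**2. What an unplanned grouping could use.** Event dates, per-sign severity, relatedness and infusion dates are all recorded, and infusions are 3 weeks apart. One could group related signs that start on an infusion date. This has three weaknesses:
- On Days 1, 22, 43 and 64 event recording is listed among the predose assessments (Sections 4.3.2.1 and 4.3.2.2). Without a clock time, a same-day sign cannot be placed before or after the infusion.
- Relatedness (Section 6.3.1.1) is to the study drug, not to the infusion. Drug-related nausea on the same day looks identical to a reaction sign.
- The worst sign grade need not equal the grade of the reaction.

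**3. Can sign-level rates give the reaction rate?** Inputs are from the label in Appendix 4, Section 6.1.
- Studies 1 and 2: 19/160 = 11.9% with a reaction (label: 12%). Listed signs are 4, 3, 3, 3, 2 and 2%, so the largest is 4% and the sum is 17%.
- Study 3: 25/167 = 15.0% (label: 15%), against 3/160 = 1.9% on placebo (label: 2%). Listed signs are 4, 4, 2, 2, 2, 2, 2 and 2%, so the largest is 4% and the sum is 20%.

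The largest sign understates the reaction rate and the sum overstates it, because one patient can have several signs. The 12% and 15% cannot be recovered from the rows. These label figures are already restricted to signs of a reaction, which the SAP rows are not.

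**4. Scale here, if the label rates applied.** There are 4 × 8 = 32 active subjects (Section 5.3). Expected number = n × p; P(at least one) = 1 − (1 − p)^n.

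| n | p | Expected | P(at least one) |
|---|---|---|---|
| 32 | 19/160 | 3.80 | 0.983 |
| 32 | 25/167 | 4.79 | 0.994 |
| 8 | 19/160 | 0.95 | 0.636 |
| 8 | 25/167 | 1.20 | 0.727 |

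The plan gives no figure of its own to reproduce. Sample size rests on clinical judgment (Section 8.1).

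**The case against.** The strongest reply has four parts.

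**The data are not unlinked.** A reader might infer that nothing connects the signs and that a count is impossible. The documents do not support that. Dates, relatedness and infusion timing are recorded, concomitant medications (Section 5.7) would show any premedication, and SAP listings are sorted by subject and date. In a trial this small, a reviewer could assemble an approximate count and a worst-sign grade. This stands, but such a count is approximate and unplanned.

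**The CRF is not among the documents.** The Section 6.3.1.2 list is not stated to be exhaustive, and a reaction field may exist. This also stands, and it conditions the fix.

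**Premedication needs no database grade.** A reader might infer that the premedication rule cannot work. It can: the investigator grades the reaction in the clinic and acts before the next infusion. What the plan does not provide is a record against which that could later be checked.

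**Sign-level recording is deliberate, and some reactions are covered.** Anaphylaxis has its own criteria (Section 6.3.4) and is not one of the three barred terms. SAP 19.1.3 gives an overall special-interest summary. Both are true. However, 19.1.3 is worded for infusion site reactions, and a query on coded terms cannot tell which chills or nausea belonged to a reaction.

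Two numerical readings should also be resisted:
- A 4% component does not mean that the largest symptom row would hold only about 32 × 0.04 = 1.3 subjects. A preferred-term row counts every case. Chills from any cause were 13% and 12% in label Table 2, or about 4 of 32.
- The 41% nausea in Section 2.3 is an on-drug oncology rate, not background. Placebo nausea in Study 3 of the label was 8%.

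**Conclusion.** The point holds in a limited form. The documents state no reaction-level flag, link, onset time, grade or derivation rule, so the number and worst grade of infusion-related reactions per dose cannot be derived reliably or by a pre-specified rule. They do not show that derivation is impossible.

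The gap would probably matter in this trial: at label rates, about 4 to 5 of 32 active subjects would react, and about 1 of 8 at a single dose. Those figures carry over rates from oncology patients at 1.8 mg/kg with median courses of 9, 7 and 15 cycles. This trial gives 4 doses and has only 8 active subjects at 1.8 mg/kg, so fewer reactions may occur. With 8 per dose any table would be descriptive. This is an inexpensive improvement to reporting; no dosing or escalation rule turns on it.

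**What to change.** Keep the sign-level entries. Unless the CRF already has them, add three items to the adverse event page: whether the sign was part of an infusion-related reaction, which infusion, and one overall grade for the reaction assigned by the investigator. An onset time would also help. If the CRF already holds these, only the protocol item list and the SAP need updating.

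In SAP Section 19.1, add a table of subjects with at least one infusion-related reaction, by worst overall grade, for each dose, all active subjects combined and placebo. Keep it separate from the infusion site reactions of 19.1.3. If the CRF can no longer be changed, write the date-and-relatedness grouping into the SAP before unblinding and label the result as approximate.

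The cost is a few CRF items and one table. No visit, procedure or treatment rule changes.
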